6.4. THE TYPE AND DURATION OF THE FOLLOW-UP OF SUBJECTS AFTER ADVERSE EVENTS

[figure not shown]
All non-mild adverse events (including serious adverse events) should be followed until the event is resolved, stabilized, or until the end of individual's participation in the study. [name] or [name] will determine a follow-up plan on a case-by-case basis based on their clinical judgment.

6.5. UNBLINDING PROTOCOL

Participants may be unblinded if there is an urgent medical need, as determined by the clinician evaluating the participant. If a participant is unblinded, study medication may be discontinued.

The following are examples of events that may result in emergency unblinding:

- -An SAE occurs that is thought to be most likely or definitely related to the study drug.
- -An AE or SAE occurs and the clinician treating the patient concludes that knowledge of the treatment arm is necessary to determine the therapy provided to the patient.
- -The study drug is accidentally ingested by a child.

6.6. DATA SAFETY AND MONITORING BOARD

The DSMB is responsible for ensuring subject safety (by reviewing blinded and unblinded safety data on a regular basis and assessing the safety of study procedures) and for monitoring the overall conduct of the study. No interim efficacy analyses will be conducted.

The DSMB is an independent group advisory to the PIs and the NIAAA, and is required to provide recommendations about starting, continuing, temporarily suspending the trial until certain conditions are met, and stopping the studies. In addition, the DSMB is asked to make recommendations, as appropriate, about:

- Benefit/risk ratio of procedures and participant burden
- Selection, recruitment, and retention of participants
- Protocol violations and adherence to protocol requirements
- Completeness, quality, and analysis of measurements
- Amendments to the study protocol and consent forms

- Participant safety
- Notification of and referral for abnormal findings

The Board will be composed of three full members (inclusive of the DSMB Chair) and 1 adjunct member. Full Members of the DSMB are:

- 1. [name] (Professor of Epidemiology and Biostatistics, BUSPH), Chair of DSMB
- 2. [name] (Professor of Medicine, Brown Medical School)
- 3. [name] (Associate Professor of Psychology, Indiana University-Purdue University Indianapolis)

This DSMB will meet every six months. In cases where Institutional Review Boards or the NIH require more frequent monitoring, procedures will be put into place to conform to those requirements. An agenda will be provided detailing the studies to be discussed. It is estimated that the meeting will be scheduled for 1.5 hours. Each protocol and data review meeting will consist of two sessions: Open Session and Closed Session. Communication in the interim will be as needed. Unscheduled meetings can be requested by any party with the responsibility of overseeing the study. Requests can be made to the DSMB Chair, PIs, or NIAAA officials. The Chair, in collaboration with the Admin Core or NIAAA, will schedule any unplanned meetings.

The DSMB will provide recommendations about temporarily suspending or stopping the study. No interim efficacy or futility analyses are planned because of the risk level of the study and because patient outcomes are very unlikely to be worse in the intervention group in the study. The study team, including the project manager, statistician, co-investigators and research associates, led by the PIs, will evaluate the progress of the study, including periodic assessments of data quality, participant recruitment, accrual and retention, and factors external to the study when interpreting the data, such as scientific developments or the new availability of proven clinical services that could have an impact on the safety of the participants, the performance of the study or the ethics of the study.

7. DATA MANAGEMENT

7.1 DATA COLLECTION

All study data will be captured electronically on netbooks via a secure, web-based data capture system with the exception of: TLFB data and daily pain diaries, which will be collected on paper calendars.

7.2 QUALITY CONTROL PROCESS

Quality control measures will include: detailed and unambiguous specifications for completion of data forms, including rules for coding skipped questions and missing data, training of study staff responsible for data collection and built-in validation rules, error checks, and question skips for electronic data

capture. All data, regardless of capture method, will be reviewed for logic, skip patterns, response ranges, and internal inconsistencies. The RAs will be queried monthly regarding any noted inconsistencies.

7.3 DATA SECURITY AND CONFIDENTIALITY

Screening forms and most other research paperwork will not include the participant's name; instead, a unique ID will be assigned to each person screened, and another number assigned to those who enroll.

Tracking information will be kept similarly. Computer data will be password protected, and accessible only to research associates needing the information for follow-up purposes.

Any documents with identifiable participant data will only be accessible to the Russian Co-Investigators (Drs. [name] and [name]), the project manager, and the RAs who recruit and follow participants, and perform QC.

Boston University School of Public Health's Biostatistics and Epidemiology Data Analytics Center (BEDAC) will design, develop and maintain the electronic data collection forms, participant and data tracking, and underlying SQL database systems, and implement procedures for data quality control, including multiple checks for entered data. Electronic data collection forms will be designed to read easily, have clear instructions, preprogrammed skip patterns, real-time range checks and internal logic to minimize missing data and result in "cleaner" data at capture.

Electronic research data will be entered directly into REDCap, which is maintained on secure BU servers. All central systems are secured physically behind two card-access doors with access to the primary door restricted to key personnel. Data will be kept indefinitely. The mastercode will be kept separate from any study data.

Assessment data will be collected directly onto computers by research assessors. Use of electronic data collection will obviate the need for double data entry and limit missing data through required fields. All data will be converted to SAS datasets and reviewed for logic, skip patterns, response ranges, and internal inconsistencies. The Boston and Russian teams will work together to resolve data issues.

7.4 WEB SYSTEMS

The study will use REDCap. REDCap is a secure web application for building and managing online surveys and databases and will be used for screening and assessments purposes. Study forms will be completed according to the schedule below.

				STUDY VISIT							
FORM	Phon e Scre en	een & ine Visit Baselin e	1 week visit	2 week visit	4 week visit	6 week visit	7 week visit	8 week visit	12 week visit	As Needed	

Pre-Screener	X										
Screener		X									
Consent and enrollment form		X									
Full assessment			X			X			X	X	
Short assessment (adherence)				X	X		X	X			
Baseline Event Form			X								
Medication visit checklist			X	X	X	X	X	X	X		
Symptom Monitoring Form				X	X	X	X	X	X		
Naloxone Challenge Form			X								
Contact info		X	X	X	X	X	X	X	X	X	X
Contact log											X
Baseline tracking form			X								
Follow-up tracking form				X	X	X	X	X	X	X	
Lab forms		X	X		X	X	X		X		
Study conclusion form											X
AE/SAE form (paper and electronic form)											X
Medication collection (paper form)			X	X	X	X	X	X	X	X	

8. STATISTICAL ANALYSIS

This study will use an intent-to-treat analysis that includes all participants according to their randomized assignment. Descriptive statistics will be calculated for variables at baseline and each follow-up time to assess whether there appear to be any differences across treatment arms.

The main focus of this aim is the assessment the impact of each intervention (naltrexone, gabapentin, or placebo) on the primary study outcome (i.e., the continuous variable change in pain severity from baseline to week 8).

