The purpose of the pilot trial is to generate preliminary data for design of a future larger RCT to demonstrate efficacy. Thus estimation rather than testing is the main objective of this aim. However we provide illustrative power calculations for our primary outcome (change in pain severity) based on prior literature and the number of participants (15 in each arm) we intend to study. It is expected that 45 participants will be enrolled into the study and less than 15% will drop out by 8 weeks. We therefore assume 39 participants (13 per arm) will complete the 8-week follow-up. The following calculations assume 2-sided tests, with an overall significance level of 0.05. For the purposes of power calculations, we consider a simple, conservative setting based on a Bonferroni adjustment for multiple comparisons, although in our analyses we will use the Hochberg sequential correction method, an approach that will result in higher power than the Bonferroni method. To maintain an overall type I error rate of 5%, we assume each of the 2 primary pairwise comparisons (i.e. each intervention vs. placebo) will be conducted at an alpha level of 0.025 for the following power calculations. Based on the 2013 study by Younger, the standard deviation for change in pain severity was 2.9. We expect the standard deviation will be similar in the proposed study and the same for each randomized group. Given this assumption, the minimum detectable difference in change in pain severity between baseline and 8 weeks that the study can detect with 80% power is 3.8 for either of the 2 primary comparisons of interest (i.e., naltrexone vs. placebo; gabapentin vs. placebo), (e.g., -3.0 vs. 0.8 for naltrexone vs. placebo, respectively) using a 2-sided t-test. Because a main goal of the study is estimation of effect sizes for the design of a future study, we also estimate the width of the confidence interval for the mean difference between any two arms for the primary outcome. Our calculations assume 2-sided 95% confidence intervals. Assuming a standard deviation of 2.9 as above, the 95% confidence interval for the mean difference in change in pain severity for either intervention arm vs. placebo would be no wider than 4.7.

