Return all unused medication to the study site.

DATE OF MANUFACTURE:

SHELF LIFE:

3.4.D. LOST OR STOLEN STUDY MEDICATION

If participants report lost or stolen medication, they will be provided with extra study medication. If participants report losing medication more than once, the study team will be alerted and the case discussed to determine a plan of action.

3.4.E. DISCONTINUATION OF STUDY MEDICATION

If as a result of study testing at week 4, a participant is found to have AST/ALT >10x normal, medications will be discontinued and the participants will be appropriately monitored for resolution of the abnormalities. If a participant has AST/ALT >5x normal as a result of study testing at week 4, participant will be rechecked at their 6-week visit to ensure levels do not increase to the threshold of discontinuation. Any participant with symptoms of acute hepatic failure (jaundice, dark urine) will have AST/ALT checked.

Those who discontinue medication will be followed and analyzed by intention to treat.

Participants found to be pregnant during the study will have their study medication discontinued, but will still be followed-up for the duration of the study. Participants who report pregnancy outside of study

visits will be instructed to immediately discontinue their study medication and requested to come in for a confirmatory urine pregnancy test.

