3.5 SCHEDULE OF DATA COLLECTION

		Scre en	Baseline Visit	1 week visit	2 week visit	4 week visit	6 week visit	7 week visit	8 week visit	12 week visit
Screening	Screening Questions	Х								
3	Verification of HIV, non-pregnancy, urine tox, and ALT/AST	Х								
Enrollment	Sign Informed Consent	Х								
Linemient	Complete contact information/verify numbers	Х								
	Randomization		Х							
	Clinical Values		Х			X			Χ	X
Laboratory	Pregnancy Test	Х	Х	X	Х	Х	Х	X		
	Urine Drug Test	Х	Х							
	AST, ALT	X				х	X (if indicat ed)			
	Creatinine	Х								
	Cold Pressor Test		Х			Х			Х	Х
	Naloxone Challenge		Х							
	Blood Draw (IL-6, IL- 1β, IL-10, TNF-alpha, CD4, HVL)		Х						х	
Assessment	Full Study Assessment		Х			Х			х	Х
	Short Assessment			Х	Х		Х	Х		
Intervention	Symptom Management/Adverse Events		×	X	Х	Х	Х	X	×	X
	Provide Medication Instructions		Х		Х	Х	Х			
	Give Study Medication		Х		Х	Х	Х			
	Discuss Adherence		Χ	Χ	Х	Χ	Х	Х	Χ	
	Assess Adherence			Χ	Х	Х	X	Х	Х	
Other	Provide Resource Card		Х							
	Compensate for Participation	Х	Х	Х	Х	Х	Х	Х	Х	Х
	Report Adverse Events		Х	Х	Х	Х	Х	Х	Х	Х
	Complete Tracking Forms	Х	Х	Х	Х	Х	Х	X	Х	Х

3.5.A. VISIT WINDOWS

Baseline Visit

Window open: 1 day post screening

• Target date: 3 days post screening

• Window close: 28 days post screening

Window length: 27 days

1 Week Visit

• Window open: 5 days post baseline

Target date: 7 days post baseline

• Window close: 10 days post baseline

• Window length: 5 days

2 Week Visit

Window open: 11 days post baseline

• Target date: 14 days post baseline

• Window close: 20 days post baseline

Window length: 9 days

4 Week Visit

Window open: 21 days post baseline

• Target date: 28 days post baseline

Window close: 37 days post baseline

Window length: 16 days

6 Week Visit

Window open: 38 days post baseline

• Target date: 42 days post baseline

• Window close: 45 days post baseline

• Window length: 7 days

7 Week Visit

• Window open: 46 days post baseline

• Target date: 49 days post baseline

• Window close: 52 days post baseline

Window length: 6 days

8 Week Visit

• Window open: 53 days post baseline

• Target date: 56 days post baseline

Window close: 73 days post baseline

Window length: 20 days

12 Week Visit

Window open: 74 days post baseline
Target date: 84 days post baseline
Window close: 94 days post baseline

Window length: 20 days

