8.1 PRIMARY ANALYSES

Descriptive statistics and graphic displays of all outcome measures will be generated.

The main analysis evaluating the impact of each intervention on the primary study outcome (i.e., the continuous variable change in pain severity and pain interference from baseline to week 8) will use multiple regression models to estimate mean differences between arms along with 95% confidence intervals. The models will include indicator variables to represent study arm. The 2 primary comparisons of interest are between each intervention vs. placebo, i.e., naltrexone vs. placebo; gabapentin vs. placebo, and will adjust for the multiple comparisons using the Hochberg sequential test procedure. We will compare naltrexone vs. gabapentin but these tests will be of secondary interest. If the data are normally distributed, multiple linear regression models will be used. However, if the distribution of change in pain severity is skewed, transformations of the data will be performed (e.g., log transformation). If an appropriate transformation is not identified, a median regression model will be used. Secondary outcomes (e.g., changes in biomarkers, cold pain tolerance) are continuous variables and will be analyzed using the same approach as above.

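### The primary model names no baseline covariate and the plan gives no missing-data assumption or method, so participants without a week-8 BPI (up to 6 of 45) drop out of it and week-4 BPI is only described

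*Combined protocol and SAP*

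**What the plan says.** Section 8 states: "This study will use an intent-to-treat analysis that includes all participants according to their randomized assignment". Section 8.1 then gives the primary analysis. The outcome is the change in BPI pain severity and interference from baseline to week 8, and the analysis "will use multiple regression models to estimate mean differences between arms along with 95% confidence intervals". On model terms it says only "The models will include indicator variables to represent study arm". Transformation or median regression is the fallback if the change is skewed, and secondary outcomes follow the same approach.

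Section 2.7.A expects that "less than 15% will drop out by 8 weeks" and continues: "We therefore assume 39 participants (13 per arm) will complete the 8-week follow-up". For people who stop medication, Section 3.4.E says "Those who discontinue medication will be followed and analyzed by intention to treat". For other time points, the only stated use in Section 8 is "Descriptive statistics will be calculated for variables at baseline and each follow-up time".

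Missing data are mentioned only as data capture: coding rules for forms (7.2) and required fields (7.3). No section names imputation, a repeated-measures model, a missingness assumption or a sensitivity analysis for missing outcomes. Week-4 BPI is collected according to Sections 2.3, 3.1, 3.6.A and the 5.2.A table.

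**The concern.** A change score needs both ends. Without a week-8 BPI there is nothing to regress, and the plan supplies no substitute, so that participant leaves the primary model even if baseline and week-4 scores are on file. The plan does not say that it accepts this, or under what assumption.

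The stated purpose of the pilot is to estimate effects for the design of a larger trial. If dropout differs between arms and is related to pain, the completer difference is biased. If baseline pain is left out, the interval may be wider than the collected data require. Both choices should be fixed before the data are seen.

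**Working it through.** **Inputs from the plan (2.7.A):** 45 randomised, 15 per arm; dropout below 15%; SD of change in pain severity 2.9; 13 completers per arm; 95% interval width no more than 4.7. No SD is given for pain interference, so the widths below concern severity only.

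**Step 1: the plan's own figures.** 45 × 0.15 = 6.75, so at most 6 losses, and 45 − 6 = 39 (13 per arm); 6/45 = 13.3%. Standard error = 2.9 × √(2/13) = 1.137. Width = 2 × t(0.975, 24) × 1.137 = 2 × 2.064 × 1.137 = 4.70. The 4.7 reproduces, so precision was planned on completers.

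**Step 2: adding baseline, then week 4.** The correlations are assumptions; the documents give none. Hold the SD of change at 2.9 with equal visit SDs s = 2.9/√(2(1−r)), where r is the baseline/week-8 correlation. Residual SD = s√(1−r²). Width = 2 × t(0.975, 23) × residual SD × √(2/13). For week 4, assume every dropout has a week-4 score, a week-4/week-8 correlation of 0.7, and a baseline/week-4 correlation of r. Variance per arm is then residual SD² × [(1−q²)/13 + q²/15], with q the partial week-4/week-8 correlation given baseline.

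| r | s | residual SD | width, baseline-adjusted | width, plus week 4 |
|---|---|---|---|---|
| 0.2 | 2.29 | 2.25 | 3.65 | 3.53 |
| 0.327 | 2.50 | 2.36 | 3.83 | 3.72 |
| 0.5 | 2.90 | 2.51 | 4.08 | 3.98 |
| 0.7 | 3.74 | 2.67 | 4.34 | 4.29 |

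Baseline does most of the work. Week 4 adds about 0.05 to 0.12.

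**Step 3: when the gain vanishes.** Var(change) = s8²(1−r²) + (s0 − r·s8)², so there is no gain when the baseline SD s0 equals r times the week-8 SD s8. Entry requires moderate to severe pain, which may narrow s0. With an assumed s0 = 1.5 and r = 0.5, 2.9² = 1.5² + s8² − 1.5·s8 gives s8 = 3.34. The residual SD is then 3.34 × √0.75 = 2.90 and the width 4.70. At r = 0.2, 0.327 and 0.7 the same s0 gives 4.45, 4.63 and 4.34.

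**Step 4: dropout bias.** This cannot be derived from the documents, so every setting here is assumed: three arms of 15, visit SD 2.5, baseline correlations 0.327, week-4/week-8 correlation 0.7, true differences −0.75 at week 4 and −1.5 at week 8, and 13.3% dropout per arm. Slopes are log-odds of dropout per point of week-4 pain. In this table every dropout has an observed week-4 BPI.

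| Dropout mechanism | change score, completers | baseline-adjusted, completers | model with week 4 |
|---|---|---|---|
| unrelated to pain | −1.48 | −1.50 | −1.49 |
| slope 1.0, all arms | −1.49 | −1.49 | −1.49 |
| slope 0.3, placebo only | −1.40 | −1.36 | −1.50 |
| slope 1.0, placebo only | −1.30 | −1.19 | −1.49 |

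With dropout unrelated to pain, the standard errors are 1.14, 0.95 and 0.92. Varying the week-4/week-8 correlation from 0.5 to 0.9 moves the change score in the placebo-only cases between −1.45 and −1.20, a bias of 0.05 to 0.30.

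The last column is the best case. At slope 1.0, placebo only, the model with week 4 gives about −1.33 to −1.36 if half the dropouts leave before week 4. If all do, it gives about −1.20, the same as baseline-adjusted completers and further from −1.5 than the change score.

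**Step 5: departures that observed scores cannot explain.** If 2 of 15 are missing in one arm and their unobserved changes differ from the rest by an assumed 1 to 3 points, the arm difference shifts by 2/15 × 1 = 0.13 to 2/15 × 3 = 0.40.

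**The case against.** A reader might infer that the plan contradicts itself by promising an analysis of everyone and then dropping people. The text does not support that. The Section 8 sentence naturally means that participants are analysed in the arm to which they were randomised, and 3.4.E reads the same way. Nor does any section call for a complete-case analysis; the omission follows from the model because nothing fills the gap.

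It can also be said that the plan works to limit loss. It follows people who stop medication, keeps the week-8 visit open late ("Window close: 73 days post baseline"), and pursues no-shows (4.7). These steps reduce missingness but do not say how the remainder is analysed, and 2.7.A still allows for it. Section 8.1 speaks of multiple regression and does not exclude covariates. That is true, but it names none.

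The strongest objection concerns size and remedy. A bias of 0.2 adds little to a standard error of 1.14: √(1.14² + 0.20²) = 1.16. A reader might also infer that using week 4 cures dropout bias. It does so only for dropouts whose week-4 score was observed, and 2.7.A says only that loss occurs by week 8. Early loss is plausible, since the dose schedule steps up over the first three weeks. Finally, the precision gain is mainly about baseline adjustment, not missing data. All of this stands, and it limits the claim without removing the gap.

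**Conclusion.** The gap is real and worth closing, but it does not invalidate the design. As written, the primary model loses up to 6 of 45 participants, has no stated missing-data assumption, and makes no inferential use of baseline as a covariate or of week-4 BPI.

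- **Precision:** width 4.7 to about 3.6 to 4.3, nearly all from baseline adjustment. This rests on equal visit SDs and assumed correlations of 0.2 to 0.7. It is nil if the baseline SD equals the correlation times the week-8 SD, approximately so at a baseline SD of 1.5 and a correlation of about 0.5.
- **Bias:** about zero with the same dropout mechanism in all arms, and 0.05 to 0.30 points in the assumed placebo-only scenarios, which is small against 4.7. The documents do not say which will occur.
- **Limit of the remedy:** if all dropouts leave before week 4, the repeated-measures model does no better than baseline-adjusted completers.

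**What to change.** For each BPI score in 8.1, make the primary analysis a likelihood-based repeated-measures model. Baseline, week-4 and week-8 BPI are outcomes, with a common baseline mean, arm-by-visit terms, unstructured covariance (3 × 4/2 = 6 parameters) and Kenward-Roger inference. Take the week-8 contrasts with placebo, keep Hochberg, and state missing-at-random. Say openly that this both adjusts for baseline and uses week 4.

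A lighter alternative keeps the 8.1 regression as primary, with baseline BPI as a covariate and multiple imputation of week 8 from arm, baseline and week-4 BPI.

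In either case:

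- Keep the 8.1 change regression, with its skewness fallback, as a sensitivity analysis.
- Add a simple sensitivity analysis for departures from missing-at-random, for example shifting the imputed week-8 values in one arm by 1 to 3 points.
- For biomarkers, CD4 and viral load, drawn only at baseline and week 8, use baseline-adjusted regression under the same stated assumption.
- Before using BPI from weeks 1, 2, 6 and 7, reconcile 2.3, 3.1 and 3.6.A, which do not list it at those visits, with the 5.2.A table, which does.

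The cost is SAP wording and modest modelling, with no new visits or data. With the repeated-measures model, the primary estimate relies on missing-at-random, normality and a covariance assumption in 45 people. It will differ from the 8.1 change regression even with complete data, and the skewness fallback moves out of the primary analysis.
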